#### Important notes for the accurate assessment of temperature:

Participants or participants' parents/legally acceptable representatives are to measure body temperature once per day, preferably always at the same time. The optimal time for measurement is the evening, when body temperature is the highest. Temperature is also to be measured at the time of any apparent fever. The observed daily temperature and the route of measurement are to be recorded in the DC, and the highest temperature will be recorded by the site in the CRF. The preferred route for this study is axillary.

#### 10.2.5.1.2 Unsolicited AE Intensity Grading Scale

For measurable unsolicited AEs that are part of the list of solicited reactions, the corresponding scale for solicited reactions will be used (see Section 10.2.5.1.1).

All other unsolicited AEs will be classified according to the following intensity scale:

- Grade 1
  - CRF: A type of adverse event that is usually transient and may require only minimal treatment or therapeutic intervention. The event does not generally interfere with usual activities of daily living.
  - DC: No interference with usual activities.
- Grade 2
  - CRF: A type of adverse event that is usually alleviated with additional therapeutic intervention. The event interferes with usual activities of daily living, causing discomfort but poses no significant or permanent risk of harm to the research participant.
  - DC: Some interference with usual activities.
- Grade 3
  - CRF: A type of adverse event that interrupts usual activities of daily living, or significantly affects clinical status, or may require intensive therapeutic intervention.
  - DC: Significant; prevents usual activities.

#### 10.3 Appendix: Contraceptive and Barrier Guidance

#### 10.3.1 Definitions

#### Woman of Childbearing Potential (WOCBP)

A woman is considered fertile following menarche and until becoming postmenopausal unless permanently sterile (see below).

If fertility is unclear (eg, amenorrhea in adolescents or athletes) and a menstrual cycle cannot be confirmed before first dose of study intervention, additional evaluation should be considered.

## Women in the following categories are not considered WOCBP

- 1) Premenarchal
- 2) Premenopausal female with 1 of the following:
  - Documented hysterectomy
  - Documented bilateral salpingectomy
  - Documented bilateral oophorectomy

For individuals with permanent infertility due to an alternate medical cause other than the above, (eg, mullerian agenesis, androgen insensitivity), Investigator discretion should be applied to determining study entry.

Note: Documentation can come from the site personnel's: review of the participant's medical records, medical examination, or medical history interview.

- 3) Postmenopausal female
  - A postmenopausal state is defined as no menses for 12 months without an alternative medical cause.
  - A high follicle-stimulating hormone (FSH) level in the postmenopausal range may be used to confirm a postmenopausal state in women not using hormonal contraception or hormonal replacement therapy (HRT). However, in the absence of 12 months of amenorrhea, confirmation with more than one FSH measurement is required.
  - Females on HRT and whose menopausal status is in doubt will be required to use one of
    the non-estrogen hormonal highly effective contraception methods if they wish to continue
    their HRT during the study. Otherwise, they must discontinue HRT to allow confirmation
    of postmenopausal status before study enrollment.

#### **10.3.2** Contraception Guidance

#### CONTRACEPTIVESa ALLOWED DURING THE STUDY INCLUDE:

**Highly Effective Methods**b **That Have Low User Dependency** *Failure rate of* < 1% *per year when used consistently and correctly.* 

- Implantable progestogen-only hormone contraception associated with inhibition of ovulationb
- Intrauterine device (IUD)
- Intrauterine hormone-releasing system (IUS) b
- Bilateral tubal occlusion
- Azoospermic partner (vasectomized or due to a medical cause)

Azoospermia is a highly effective contraceptive method provided that the partner is the sole sexual partner of the woman of childbearing potential and the absence of sperm has been confirmed. If not, an additional highly effective method of contraception should be used.

Note: documentation of azoospermia for a male participant can come from the site personnel's review of the participant's medical records, medical examination, or medical history interview.

**Highly Effective Methods**b **That Are User Dependent** *Failure rate of* < 1% *per year when used consistently and correctly.* 

- Combined (estrogen- and progestogen-containing) hormonal contraception associated with inhibition of ovulationc
  - oral
  - intravaginal
  - transdermal
  - injectable
- Progestogen-only hormone contraception associated with inhibition of ovulationc
  - oral
  - injectable
- Sexual abstinence

Sexual abstinence is considered a highly effective method only if defined as refraining from heterosexual intercourse during the entire period of risk associated with the study intervention. The reliability of sexual abstinence needs to be evaluated in relation to the duration of the study and the preferred and usual lifestyle of the participant.

**Effective Methods**d That Are Not Considered Highly Effective Failure rate of  $\geq 1\%$  per year when used consistently and correctly.

- Progestogen-only oral hormonal contraception where inhibition of ovulation is not the primary mode of action
- Male or female condom with or without spermicide
- Cervical cap, diaphragm, or sponge with spermicide
- A combination of male condom with either cervical cap, diaphragm, or sponge with spermicide (double-barrier methods)c
- a) Contraceptive use by men or women should be consistent with local regulations regarding the use of contraceptive methods for those participating in clinical studies.
- b) Failure rate of <1% per year when used consistently and correctly. Typical use failure rates differ from those when used consistently and correctly.
- c) [Male condoms must be used in addition to hormonal contraception].
- d) Considered effective, but not highly effective failure rate of ≥1% per year. Periodic abstinence (calendar, symptothermal, post-ovulation methods), withdrawal (coitus interruptus), spermicides only, and lactational amenorrhea method (LAM) are not acceptable methods of contraception.
- e) Male condom and female condom should not be used together (due to risk of failure from friction).

## 10.4 Appendix: Risk-based Approach

ICH E6-R2 guideline for GCP is introducing the « risk-based approach » concept which permits to focus efforts on what is critical for a study and most specifically on Critical Data and Critical Processes. Critical data and processes are defined for the study with associated risks in the Study Risk Management Plan.

## 10.5 Appendix: Abbreviations

AE Adverse event
AF Assent form

AESI Adverse event of special interest

AR Adverse reaction
BL Blood sample

CDISC Clinical Data Interchange Standards Consortium

CI Confidence interval

CIOMS Council for International Organizations of Medical Sciences

COVID-19 Coronavirus disease 2019

CRF Case report form

CRO Contract Research Organization

DC Diary card

DNA Deoxyribonucleic acid

EU European Union FAS Full analysis set

FSH Follicle-stimulating hormone GCI Global Clinical Immunology

GCP Good Clinical Practice

GDPR General Data Protection Regulation

GMT Geometric mean titer

GPV Global Pharmacovigilance

HIPAA Health Insurance Portability and Accountability Act

HPV human papillomavirus

HRT Hormonal replacement therapy

hSBA Serum bactericidal assay using human complement

IB Investigator's Brochure
ICF Informed consent form

ICH International Council for Harmonisation

IEC Independent Ethics CommitteeIMD Invasive meningococcal disease

IMP Investigational medicinal product

IRB Institutional Review Board

ITP Idiopathic thrombocytopenic purpura

ITT Intent-to-treat

LLOQ Lower limit of quantification

MCV4-CRM Meningococcal conjugate vaccine quadrivalent MedDRA Medical Dictionary for Regulatory Activities

NIMP Non-investigational medicinal product
NSAID Non-steroidal anti-inflammatory drug

PP Per protocol

PPAS Per-protocol analysis set

RCDC Reverse cumulative distribution curve

RMO Responsible Medical Officer

RNA Ribonucleic acid

SAE Serious adverse event SafAS Safety analysis set

SAP Statistical analysis plan SoA Schedule of activities

SUSAR Suspected unexpected serious adverse reaction

TC Telephone call

Tdap tetanus, diphtheria, and acellular pertussis

US(A) United States (of America)

WOCBP Woman of Childbearing Potential

Children aged 2 through 11 years	20
Table 4.3 : Solicited injection site reactions: terminology, definitions, and intensity scales –	
Adolescents and adults aged ≥ 12 years	21
Table 4.4 : Solicited systemic reactions: terminology, definitions, and intensity scales – Infants	
and toddlers aged ≤ 23 months	22
Table 4.5: Solicited systemic reactions: terminology, definitions, and intensity scales - Children	ı
aged 2 through 11 years, adolescents or adults aged \geq 12 years	23

List of Figures

1 Overall Design

[figure not shown]
The design of the table is summarized in Table 1.1.

Table 1.1: Overall design

Type of design	Single group, single-center	
Phase	III	
Control method	Uncontrolled	
Study population	Meningococcal vaccination naïve, healthy toddlers, children, adolescents, adults and older adults aged 12 months and above	
Level and method of blinding	Open-label	
Study intervention assignment method	Not applicable	
Number of participants		
Intervention groups	All eligible participants will receive a single intramuscular injection of MenACYW conjugate vaccine	
Total duration of study participation	The duration of each participant's participation will be approximately 30 to 44 days	
Country	Vietnam	
Use of an Independent Data Monitoring Committee, Dose Escalation Committee, or similar review group	No	

The study design of MEQ00074 study is presented in Figure 1.1.

Figure 1.1: Graphical study design

BL: blood sample; TC: telephone call; VAC: vaccination

The schedule of activities are given in Table 1.2

Table 1.2: Schedule of activities

Phase III Study, 2 Visits, 2 Telephone calls, 1 Vaccination, 2 Blood Samples, 30 to 44 Days' Duration Per Participant

Visit/Contact	Collection of information in the CRF	Visit 1	TC1	TC2	Visit 2
Study timelines (days)		D01	D04 Visit 1 + 3 days	D09 Visit 1 + 8 days	D31 Visit 1 + 30 days
Time windows (days)		-	+2 days	+2 days	+14 days
Visit procedures:					
Informed consent/assent*	X	X			
Inclusion/exclusion criteria	X	X			
Collection of demographic data	X	X			
Urine pregnancy test (if applicable)		X			
Collection of significant medical history	X	X			
Physical examination (including prevaccination temperature)**		X			
Review of temporary contraindications for blood sampling †	X				X
Blood sampling (BL) ‡ [3 mL]	X	BL0001			BL0002
Vaccination	X	X			
Immediate surveillance (30 min)	X	X			
Information on DC provided		X			
Telephone call (TC) §	X		X	X	
Collection of solicited injection site and systemic reactions**	X	Day 1 to Day 8			
Collection of unsolicited AEs	X		Visit 1	to Visit 2	
DC reviewed and information collected					X
Collection of reportable concomitant medications	X	X			X
Collection of SAEs, including AESIs ††	X	To be reported at any time during the study period			
Collection of pregnancies	X	To be rep	ported at any tir	ne during the st	udy period
End of study participation record ‡‡	X				X

Abbreviations: AE: adverse event; AESI: adverse events of special interest; BL: blood sampling; CRF: case report form; DC: diary card; SAE: serious adverse event; TC: telephone call

^{*} Assent required for participants aged 12 to 15 years.

^{**}Physical examination should be performed as per standard of care. If a routine examination had been performed within the last week by the Investigator, a sub-Investigator, or a licensed nurse practitioner, it does not need to be repeated unless there were some changes in health status, in which case it may be limited to the affected area. Temperature needs to be measured before vaccination and daily during the 7 days after vaccination and recorded in the DC.

†Should a participant receive oral or injectable antibiotic therapy within 3 days prior to any blood draw, the Investigator will postpone that blood draw until it has been 3 days since the participant last received oral or injectable antibiotic therapy. Postponement must still be within the timeframe for blood draw. If postponement would result in the sample collection falling outside of this timeframe, the blood sample should be collected without postponement, and it should be appropriately documented that the sample was taken less than 3 days after stopping antibiotic treatment.

‡Blood sample at Visit 1 to be drawn before administration of the vaccine.

§The first telephone call will be made 3 days to 5 days after the vaccination. The second telephone call will be made 8 days to 10 days after the vaccination. If Day 04 (+ 2 days) and Day 09 (+2 days) fall on a weekend or holiday, the telephone call may be made on the following business day. During this telephone call, the staff will find out whether the participant experienced any SAE (including any AESI) not yet reported, and will remind the participant/participant's parent/legally acceptable representative to continue using the DC, bring the DC to the study center at the next visit, and confirm the date and time of the next visit.

** Solicited injection site and systemic reactions will be recorded from the day of vaccination through 7 days after vaccination.

††AESI will be collected throughout the study as SAEs to ensure that the events are communicated to the Sponsor in an expedited manner and followed up until the end of the follow-up period or resolution, as per the assigned causal relationship

‡‡ In case of participant discontinuation at a visit, the entire visit will be completed.

2 Objectives and Endpoints

The study objectives and the corresponding endpoints are described in Table 2.1.

Table 2.1: Objectives and endpoints

Objectives		Endpoints	
Immunogenicity	7		
meningo before ar	ribe the antibody responses to occcal serogroups A, C, W, and Y and 30 days after the administration alle dose of MenACYW conjugate	Antibody titers against meningococcal serogroups A, C, W, and Y measured by serum bactericidal assay using human complement (hSBA) will be assessed before and 30 days after vaccination with a single dose of MenACYW conjugate vaccine.	
Safety			
	ribe the safety profile of a single MenACYW conjugate vaccine	The safety profile will be evaluated within 30 days (+14 days) after vaccination. The following endpoints will be used for the evaluation of safety: • Presence of any unsolicited systemic adverse events (AEs) reported in the 30 minutes after vaccination • Presence of solicited (prelisted in the participant's diary card [DC] and case report form [CRF]) injection site and systemic reactions starting any time from the day of vaccination through 7 days after vaccination • Presence of unsolicited (recorded in a DC) non-serious AEs up to 30 days after vaccination; unsolicited non-serious AEs occurring after D31 will be presented in a specific listing • Presence of serious adverse events (SAEs) (including adverse events of special interest [AESIs]) throughout the study, ie from D01 (vaccination) to the last study day D31; SAEs occurring after D31 are also to be reported if they are considered related to vaccination with the investigational medicinal product (IMP) Depending on the items, the endpoints recorded or derived could include: nature (Medical Dictionary for Regulatory Activities [MedDRA] preferred term), time of onset, duration/number of days of occurrence, intensity, relationship to the vaccine, whether the AE led to early termination from the study, outcome, and seriousness criterion	

3 Statistical Considerations

3.1 Statistical Hypotheses

No statistical hypotheses will be tested. Descriptive statistics will be presented.

3.2 Sample Size Determination

There are no statistically powered hypotheses in this study. No formal sample size calculations were performed.

A total of 446 participants will be enrolled in the study, 223 participants will be enrolled in age category 12 months to 23 months, 223 participants will be enrolled in age category 24 months and above. An estimated 10% non-adherence rate from enrollment will result in approximately 400 evaluable participants in total, and 200 evaluable participants in each age category (12 months - 23 months, \ge 24 months).

The overall evaluable study cohort (N=400) will provide a probability of approximately 95% of observing any AE (at least 1 occurrence) with a true incidence of 0.75%.

For participants aged 12 to 23 months, 200 participants will provide a probability of approximately 95% of observing any AE (at least 1 occurrence) with a true incidence of 1.5%.

For participants aged 24 months and above, 200 participants will provide a probability of approximately 95% of observing any AE (at least 1 occurrence) with a true incidence of 1.5%.

3.3 Populations for Analyses

The following populations are defined for immunogenicity and safety analyses:

Analysis Set	Description	
	Participants who have received the study vaccine and have any safety data available.	
•	Participants who received the study vaccine and had a valid post-vaccination serology result.	
	etSubset of the FAS. Participants presenting with at least one of the following	
(PPAS)	relevant protocol deviations will be excluded from the PPAS:	
	 Participants did not meet all protocol-specified inclusion criteria or at least one of the protocol-specified exclusion criteria 	

- Participant did not receive vaccine
- Preparation and / or administration of vaccine was not done as perprotocol
- Participants did not provide the post-dose serology sample at Visit 2 in the proper time window or a post-dose serology sample was not drawn
- Participants received a category 2 or 3 protocol-prohibited therapy / medication / vaccine
- Participants had other protocol violations that affected the participant's immune response, as determined by the clinical team before locking the database.

In addition to the reasons listed above, participants will also be excluded from the PPAS if their Visit 2 serology sample did not produce a valid test result.

3.4 Statistical Analyses

3.4.1 General Considerations

Safety and immunogenicity parameters will be analyzed in specified analysis sets in the overall population, as well as by age categories (12 months -23 months, ≥ 24 months).

The statistical analyses will be performed under the responsibility of the Sponsor's Biostatistics platform using SAS® Version 9.4 or later.

For descriptive purposes, the following statistics will be presented:

Table 3.1: Descriptive statistics produced

Disposition and follow-	Categorical data	Number of participants.		
up description		Percentage of participants.		
	Continuous data	Mean, standard deviation, quartiles, minimum and		
		maximum.		
Baseline characteristics	Categorical data	Number of participants.		
		Percentage of participants.		
	Continuous data	Mean, standard deviation, quartiles, minimum and		
		maximum.		
Clinical safety results	Categorical data	Solicited: Number and percentage (95% CIs for		
		main endpoints) of participants.		
		Unsolicited: Number and percentage (95% CIs for		
		main endpoints) of participants and number of		
		events.		
Immunogenicity results	Categorical data	Number and percentage (95% CIs for main		
	(seroprotection,	endpoints) of participants.		
	seroconversion, cutoff)			
	Continuous data	Log10: Mean and standard deviation.		
	(titer / data†)	Anti-Log10 (work on Log10 distribution, and anti-		
		Log10 applied): Geometric mean, 95% CI of the		
		geometric mean, quartiles, minimum, and		
		maximum.		
		Graphical representation by Reverse Cumulative		
		Distribution Curve (RCDC).		

The confidence interval (CI) for the single proportion will be calculated using the exact binomial method (Clopper-Pearson method), quoted by Newcombe (1), i.e., using the inverse of the beta integral with SAS®.

For immunogenicity results, assuming that Log10 transformation of the titers / data follows a normal distribution, at first, the mean and the 95% CI will be calculated on Log10 (titers / data) using the usual calculation for normal distribution (using Student's t distribution with n-1 degree of freedom), then antilog transformations will be applied to the results of calculations, in order to provide geometric means (GMs) and their 95% CI.

3.4.2 Immunogenicity Endpoint

No statistical hypotheses will be tested. Descriptive statistics will be provided for the antibody titers against meningococcal serogroups A, C, W, and Y by using hSBA before and 30 days after a single dose of meningococcal conjugate vaccine.

.

All immunogenicity analyses will be performed on the PPAS and the FAS.

In general, categorical variables will be summarized and presented by frequency counts, percentages, and CIs. The 95% CIs of point estimates will be calculated using the normal approximation for quantitative data and the exact binomial distribution (Clopper-Pearson method) for percentages. For GMTs, 95% CIs of point estimates will be calculated using normal approximation assuming they are log10-normally distributed.

Descriptive analyses of antibody responses to A, C, W, and Y serogroups using hSBA will include but not be limited to:

- hSBA seroprotection rate (titer $\geq 1:8$) and 95% CI
- GMTs and 95% CI.
- Titer distribution and reverse cumulative distribution curves (RCDCs)
- Percentage of participants with titers ≥ 4-fold rise from pre-vaccination to post-vaccination, and 95% CI
- Percentage of participants with hSBA titers \geq 1:4, and 95% CI
- Percentage of participants with hSBA vaccine seroresponse, and 95% CI Note: hSBA vaccine seroresponse for serogroups A, C, W, and Y is defined as:
- For a participant with a pre-vaccination titer < 1:8, the post-vaccination titer must be $\geq 1:16$
- \circ For a participant with a pre-vaccination titer $\geq 1:8$, the post-vaccination titer must be at least 4-fold greater than the pre-vaccination titer

3.4.3 Safety Endpoint

No statistical hypotheses will be tested.

Safety results will be described for participants in the study. The main parameters for the safety endpoints will be described by 95% CIs (based on the Clopper-Pearson method).

Depending on the items, the endpoints recorded or derived could include: nature (Medical Dictionary for Regulatory Activities [MedDRA] preferred term), time of onset, duration/number of days of occurrence, intensity, relationship to the vaccine, whether the AE led to early termination from the study, outcome, and seriousness criterion.

All safety analyses will be performed on the SafAS.

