#### Follow-up of Discontinuations

For participants who have prematurely terminated the study, the site should attempt to contact them and complete all scheduled safety follow-ups, except if they specified that they do not want to be contacted again and it is documented in the source document.

For participants where the reason for early termination is lost to follow-up, the site will not attempt to obtain further safety information. See Section 7.3 for definition of "lost to follow-up".

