3.4.4 Handling of Missing Data and Outliers

3.4.4.1 Safety

Generally, no replacement will be done for Safety Missing Data and Outliers.

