4.2.1.1.3 Presence

Presence is derived from the maximum overall intensity over the time period considered:

- None: No presence
- Grade 1, Grade 2, or Grade 3: Presence
- Missing or Unknown: Missing presence

Participants with at least one non-missing presence for a specific endpoint will be included in the analysis. Conversely, those without a non-missing presence will not be included in the analysis of the endpoint.

The time period is displayed as D1-D4, D5-D8, D9 and later.

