4.2.1.2 Unsolicited AEs

4.2.1.2.1 Presence

An observation will be considered an event if it has at least a verbatim term and is not a Grade 0 intensity event.

Grade 0 events are not included in safety analysis but are included in separate listings.

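### The 30-day unsolicited AE endpoint has no participant-level missing state, so vaccinees with no AE recorded and no follow-up after the 30-minute observation count as AE-free

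*SAP*

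**What the plan says.** SAP 3.4.3 assigns every safety endpoint to one set: "All safety analyses will be performed on the SafAS". SAP 3.3 defines that set as "Participants who have received the study vaccine and have any safety data available", with no minimum follow-up and no diary requirement. Protocol 8.3.1 keeps all vaccinees under observation for 30 minutes, and the schedule has this surveillance entered in the CRF.

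The endpoint at issue is unsolicited non-serious AEs up to 30 days, recorded in a diary card (SAP Table 2.1). The schedule of activities puts diary review at Visit 2 only (D31, +14 days). Its footnote describes the calls at D04 and D09 as asking about SAEs and AESIs and giving reminders.

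For unsolicited AEs, SAP 4.2.1.2.1 says: "An observation will be considered an event if it has at least a verbatim term and is not a Grade 0 intensity event". For solicited reactions, SAP 4.2.1.1.3 has a missing category and says "those without a non-missing presence will not be included in the analysis of the endpoint". SAP 3.4.4.1 adds: "Generally, no replacement will be done for Safety Missing Data and Outliers".

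Protocol 7.2 (Follow-up of Discontinuations) tells sites to attempt the scheduled safety follow-up of early terminations unless contact is refused, but then says: "For participants where the reason for early termination is lost to follow-up, the site will not attempt to obtain further safety information".

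**The concern.** The unsolicited rule classifies records, not participants. With no record there is no event, and nothing separates a participant who was followed and had no AE from one who was never asked. The missing-data rules in SAP 3.4.4.1.1 to 3.4.4.1.5 and 4.2.1.2.4 concern fields of an AE that has already been reported; none covers a participant with no follow-up. Such a participant leaves the solicited denominators but stays in the unsolicited one as a 30-day non-event.

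Safety is one of two objectives, and the study has a single arm. The reported percentage with its Clopper-Pearson interval is itself the result, and no comparator arm exists in which an under-count could cancel. Unobserved people counted as non-events move the estimate down and make the interval slightly too narrow.

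**Working it through.** **The plan's own figures.** SAP 3.2 gives 446 enrolled (223 per age category), 10% non-adherence and about 400 evaluable: 446 × 0.9 = 401.4 and 223 × 0.9 = 200.7. The detection probabilities reproduce: 1 − (1 − 0.0075)^400 = 95.1% and 1 − (1 − 0.015)^200 = 95.1%.

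**Assumed inputs.** The documents give none of these:
- p, the true 30-day risk of an unsolicited non-serious AE: 20% for illustration.
- d, the share of the SafAS lost before any such information is collected: 2%, 5% or 10%.
- c, the share of lost participants' AEs captured anyway: 0, then 50%.

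**Formula.** If loss is unrelated to AEs, the expected SafAS rate is p × (1 − d(1 − c)). With c = 0 the relative shortfall is d. If loss is related to AEs, the absolute shortfall is d times the AE risk among those lost, so it cannot exceed d.

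**Expected rate at p = 20%**

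| d | c = 0 | c = 50% |
|---|---|---|
| 2% | 19.6% | 19.8% |
| 5% | 19.0% | 19.5% |
| 10% | 18.0% | 19.0% |

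**Worked counts, N = 446, c = 0**

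| Lost | Followed | With AE | SafAS denominator (95% CI) | Followed only (95% CI) |
|---|---|---|---|---|
| 9 (2%) | 437 | 87 | 19.5% (15.9–23.5) | 19.9% (16.3–24.0) |
| 22 (5%) | 424 | 85 | 19.1% (15.5–23.0) | 20.0% (16.3–24.2) |
| 45 (10%) | 401 | 80 | 17.9% (14.5–21.8) | 20.0% (16.1–24.2) |

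In the 10% row, if all 45 lost participants had had an AE, the rate would have been (80 + 45)/446 = 28.0%.

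**Coverage of the nominal 95% interval.** This sums Binomial(followed, 0.20) probabilities over the counts whose Clopper-Pearson interval, built with the full SafAS denominator, contains 20% (c = 0).

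| Loss | Pooled, N = 446 | One age category, N = 223 |
|---|---|---|
| 2% | 95.2% | 96.3% |
| 5% | 92.9% | 95.3% |
| 10% | 83.1% | 91.4% |

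The standard error at 401 followed is √(0.2 × 0.8/401) = 2.0 points, so the 10% shift is about one standard error. At 2% loss it is about 0.2 of one.

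**Detection probabilities.** With 10% loss and nothing captured, 1 − (1 − 0.0075 × 0.9)^446 = 95.1% and 1 − (1 − 0.015 × 0.9)^223 = 95.2%. The plan's claim already uses the reduced N and is unaffected.

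**The case against.** Much can be said for leaving the plan alone.

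- **Few participants are affected.** Protocol 7.2 asks sites to complete safety follow-up of early terminations and expects withdrawal to be uncommon. Protocol 7.3 requires repeated contact attempts before anyone is called lost. Footnotes to the schedule have the whole visit completed when a participant discontinues at a visit. This stands. A reader might infer that everyone who leaves before diary review is scored AE-free; the documents do not support that. AEs already recorded still count, and SAP 4.2.2.6 provides for those that lead to discontinuation. The gap is mainly loss to follow-up, refusal of contact and diaries never recovered.
- **Some information may still arrive.** Unsolicited AE collection runs from Visit 1 to Visit 2, the calls are recorded in the CRF, and Protocol 8.3.2 has participants interviewed at intervals. Nothing bars recording a non-serious AE mentioned in a call. This stands, and makes c = 0 the unfavourable case.
- **The solicited rule is lenient too.** One non-missing presence keeps a participant in, and SAP 4.2.1.1.1 converts a recorded absence with all daily records missing to None (except fever). This stands: the two rules diverge only for participants with no solicited data at all, so it would be too strong to say they are opposed throughout.
- **Dropout will be visible.** Disposition will be tabulated. That helps, but it does not show how many SafAS non-events lack 30-day AE follow-up.
- **The denominator is inferred.** The SAP does not state it in so many words for this endpoint. That is a reason to state it.

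**Conclusion.** The gap is real and minor. As written, a SafAS member with no AE recorded and no unsolicited AE information after the 30-minute observation counts as AE-free for 30 days, and this can only lower the reported rate.

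The size rests on assumptions. At 20% incidence with nothing captured it is about −0.4 point at 2% loss (coverage about 95%), −1.0 point at 5% (about 93% pooled, 95% per age category) and −2.0 points at 10% (about 83% pooled, 91% per age category). Capturing half of the lost participants' AEs halves the shifts.

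A reader might take the 83% as the expected performance of the interval. It needs 10% loss, zero capture and the pooled sample together, and SAP 3.2 does not describe dropout: "An estimated 10% non-adherence rate from enrollment will result in approximately 400 evaluable participants in total". That allowance also covers per-protocol deviations in participants who were fully followed for safety, so 10% loss is a ceiling. The detection probabilities stand, and no hypothesis test is affected because none is planned.

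**What to change.** In SAP 3.4.3 and 4.2.1.2.1:

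1. Keep the SafAS row as the main result, and say that its denominator for unsolicited AEs is the whole SafAS. Keep the full SafAS for immediate AEs, SAEs and AESIs.
2. For 30-day unsolicited non-serious AEs, report overall and by age category how many SafAS participants lack a reviewed diary card or a safety contact at or after D31.
3. Add one supplementary row whose denominator excludes only SafAS participants with no recorded AE and no unsolicited AE information after the 30-minute observation. Every reported AE, including those in early leavers, then stays in the numerator. Restricting the row to participants followed to D31 would discard known AEs and should be avoided.

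The cost is SAP wording, one derived flag from data already collected, and one extra row with a slightly wider interval. The supplementary rate may be slightly high, because leavers with an AE are kept while unobserved leavers are not. It should be read together with the SafAS row, which is slightly low.
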